Medical University of South Carolina Protocol

PI Name: [name]

Study Title: Effects of Neuromodulation and Rehabilitation of the Locomotor Network in Freezing of Gait

TABLE OF CONTENTS –

- A. Specific Aims, page 1
- B. Background and Significance, page 1-2
- C. Preliminary Studies, page 2
- D. Research design and methods, page 2
- E. Protection of Human Subjects, page 3
- F. References, page 8
- G. Consultants, page 8
- H. Facilities Available, page 8
- I. Investigator Brochure, page 10
- J. Appendix, page 10

A. SPECIFIC AIMS

Aim 1: To determine the effects of supplementary motor area low frequency repetitive transcranial magnetic stimulation (SMA LF-rTMS) + rehabilitation compared to rehabilitation alone on the locomotor network in patients with PD and FoG.

Hypothesis: SMA LF-rTMS followed by rehabilitation will decrease connectivity between mesencephalic locomotor region (MLR) and SMA more so than rehabilitation alone.

Aim 2: To determine the effects of SMA LF-rTMS + rehabilitation compared to rehabilitation alone on FoG severity in patients with PD and FoG.

Hypothesis: SMA LF-rTMS followed by rehabilitation will improve FoG severity (as measured by objective and subjective markers of FoG severity) more so than rehabilitation alone.

B. BACKGROUND AND SIGNIFICANCE

FoG is a debilitating condition, which occurs in the majority of patients with PD¹⁻³. FoG often leads to falls, hospitalizations, or nursing home placement and has been found to be the most important predictor of poor health-related quality of life^{2,4-6}. Current treatment strategies aim to optimize response to available medical or surgical therapies; however, responses are limited, inconsistent and short lived. Previous rehabilitation strategies have yielded only modest improvements in gait parameters not FoG specifically, and there is no evidence of sustained efficacy. As our knowledge of the pathophysiology grows, we begin to understand that FoG is not purely a dopaminergic circuit phenomenon. Preliminary evidence from our group and others support the notion that FoG is a network dysfunction with significant contribution from cortical structures. Our observation of the reversibility of FoG following immobilization supports the plausibility of network modulation and rehabilitation as a therapeutic approach.

By characterizing locomotor network dysfunction in FoG before and after cortical inhibition and rehabilitation we can provide further evidence of increased cortical governance as a major contributor to

the pathophysiology of FoG. Furthermore, the pilot data gathered here will not only support the feasibility of neuromodulation of the locomotor network, but will support the use of cortical inhibition as a therapeutic approach to FoG. We believe that with our current understanding of the locomotor network, we can target the supplementary motor area (SMA) in a non-invasive way with rTMS, and normalize locomotor network activity. This approach will mimic the immobilization periods, releasing cortical control in a targeted manner. Once this maladaptive process is removed, patients will be primed to walk without cortical interference. This provides a therapeutic window where rehabilitative approaches designed to increase automatic gait. By performing this combined cortical inhibition and gait training repeatedly we propose we will achieve network normalization and reverse FoG while gaining considerable knowledge regarding FoG pathophysiology, neuromodulation and rehabilitation.

C. PRELIMINARY STUDIES

Preliminary Studies: We performed functional and diffusion MRI on 46 patients with PD, 22 patients with FoG and 24 PD controls. There was increased functional connectivity between PPN and multiple structures (including the SMA) within the motor network in FoG compared to PD-controls (see figure 1). We also found a significantly increased fiber count with diffusional kurtosis imaging (DKI) based tractography on tracts originating in the left PPN and ending in the SMA (see figure 2). Overall our data demonstrates the feasibility of the use of functional and structural MRI for evaluating these networks in our hands, as well as supporting the central hypothesis of increased cortical control.

We looked at dual task interference for velocity, step length, time to turn and overall task time on 23 subjects from our cohort that had full set of gait analysis data. We found dual task interference to be greater in patients with FoG compared to PD controls, particularly in the off medication state, and for the overall task and turning task (see Figure 3). This data supports the notion that dual task interference, particularly for turning is an important marker for FoG severity, and can be used as an effective outcome measure in our study.

D. RESEARCH DESIGN AND METHODS (including data analysis)

Imaging Protocol: Subjects will undergo identical imaging protocols before and after intervention. For **structural imaging** deterministic fiber-tracking algorithm based on DKI will be used, with a seeding region placed at the PPN to the ending region at the SMA. The anisotropy threshold for all subjects will be set at 0.20, angular threshold at 40 degrees, and step size at 1.5 mm. Tracks with length less than 60 mm were discarded and a total of 10000 seeds were placed. For **fMRI**, subjects will have eyes closed at rest (resting state or RS fMRI). BOLD time series will be extracted via SPM 12's marsbar toolbox from predetermined regions of interest (ROIs) including the left PPN, STN, pallidum, cerebellum, putamen, caudate, primary motor cortex, SMA, and thalamus. Time course correlations will be performed to determine a correlation coefficient between the PPN and locomotor network ROIs. For the **interleaved TMS/BOLD protocol** patients will lay supine in the MRI scanner with a TMS coil mounted in the MR head coil. Resting motor threshold (RMT) will be obtained, and the coil will be adjusted from the motor cortex to the SMA. Participants will then receive a run of TMS/BOLD (12 single pulses with 12 second interpulse interval at 110% RMT).

[figure not shown]

Figure 1.

[figure not shown]

Figure 2.

[figure not shown]

Figure 3.

Table 1
Summary of Activities:
Screening Visit
Cognitive Assessment
Questionnaires
Baseline Gait Analysis
Baseline MRI Visit
RS fMRI
Diffusion MRI
Interleaved TMS/BOLD
Intervention x 10 days
1Hz rTMS
Dual task training
Treatment questionnaire (day 10 only)
Post-Tx Gait Analysis
Post-Tx MRI Visit
Phone assessments (nFOGQ 1, 2 & 3 months)

Patient Selection: Subjects meeting diagnostic criteria for PD and documented FoG will be recruited from the MUSC Movement Disorder Clinic by clinical staff. Subjects with contraindications to MRI, or TMS (no history of seizures, no metal implants in head, no pregnancy) dementia, or inability to complete the walk 30 feet in the off state without assistance will be excluded. Questionnaires to assess cognitive, quality of life (PDQ39) and FoG assessments (nFOG-Q⁷) will be administered at screening visit and post intervention. Standard motor (Unified PD rating scale; UPDRS) assessments will be performed at the time of gait analysis (see Table 1). Women of childbearing potential will have a urine pregnancy test.

rTMS Protocol: Active rTMS will be delivered to the bilateral SMA region at the following parameters: 1 Hz, 1200 total pulses, 110% resting motor threshold (rMT), 20 minutes total for ten total sessions. Sham stimulation will be administered using the Magventure B-65 placebo system in which the sham side of the coil was placed over the pre-SMA (no magnetism delivered) and electricity is delivered to scalp stimulating electrodes in the same pulse sequence as active stimulation replicating stimulation sensation. This device is FDA approved for Depression. Participants will be given a questionnaire to complete about their thoughts on the treatment. This will occur on the last day of the intervention period (10th day of intervention).

Rehabilitation Protocol: Subjects will undergo ten, 20 minute, dual task training sessions immediately following each rTMS session. Dual task training will consist of repetitive trials of straightaway walking and turning while adding increasingly difficult concurrent cognitive tasks (working memory language and calculation). Subjects will be instructed to focus on the cognitive task, not on their gait with the goal of improving gait without increasing error rate on the cognitive task. Variations of this protocol have been successfully implemented in this patient population^{8,9}.

Trial Design and outcomes: Subjects will be randomized to either active rTMS + rehabilitation or rehabilitation alone at a 2:1 ratio (10 active: 5 control). An additional 6 patients will be randomized to either active rTMS + rehabilitation or rehabilitation alone at a 1:2 ratio (2 active: 4 control). This will bring total number of subjects to 12 active and 9 control. The primary outcome measure will be dual task interference for turning.

Gait Assessment/Analysis Protocol: Gait is assessed at baseline and post intervention. Subjects will walk on an electronic walkway (GaitRite + M²) which will capture straightaway walking and turning, in the off medication and on medication state, under single and dual task conditions (2 trials each), capturing multiple spatiotemporal parameters. Dual task interference for overall task time (timed up and go), step length, velocity and nFOG-Q scores will be secondary outcomes. Gait assessment will be videotaped.

Statistical analyses: The sample size estimation is based on the primary (mechanistic) aim (Aim 1), since the effect size of the clinical aim (Aim 2) has not yet been established. A two group t-test with a 0.05 two-sided significance level will have 80% power to detect the difference between a treatment group mean of 0.11 and a control group mean of -0.06 assuming that the standard deviation is 0.10, when the sample sizes in the two groups are 12 and 9, respectively (a total sample size of 21). The mean and standard deviation estimates are based upon the functional connectivity strength for the FOG+ and combined control groups as reported in Fling et al 2014¹⁰. The observed treatment effects on FoG severity of the treatment group, as compared to the control group, will be used to determine the effect size of this therapy, and estimate the sample size for future trials aiming to determine efficacy.

E. PROTECTION OF HUMAN SUBJECTS

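### The chance of active treatment differs between the two randomised cohorts (10:5, then 2:4), and no outcome, including the primary, has a cohort or baseline adjustment specified

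*Combined protocol and SAP*

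**What the plan says.** Section D, Trial Design and outcomes, sets two allocation ratios. The first 15 patients are randomised 2:1, giving 10 active and 5 control. Then: "An additional 6 patients will be randomized to either active rTMS + rehabilitation or rehabilitation alone at a 1:2 ratio (2 active: 4 control"). The two sets are added together: "This will bring total number of subjects to 12 active and 9 control". The same paragraph names the primary outcome: "The primary outcome measure will be dual task interference for turning".

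Section D, Statistical analyses, is the only statistical text. Its one named test, "A two group t-test with a 0.05 two-sided significance level", appears inside the power statement for 12 and 9 patients, and that statement concerns connectivity: "The sample size estimation is based on the primary (mechanistic) aim (Aim 1"). For freezing severity (Aim 2), the observed difference between arms "will be used to determine the effect size of this therapy, and estimate the sample size for future trials".

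Before-and-after data are collected. The gait section says "Gait is assessed at baseline and post intervention", imaging is done before and after the intervention, and the freezing questionnaire is given at screening and afterwards. The Aim 1 hypothesis is worded as change: "SMA LF-rTMS followed by rehabilitation will decrease connectivity between mesencephalic locomotor region (MLR) and SMA more so than rehabilitation alone". No section defines a change score, a baseline covariate, a stratified analysis or a cohort term.

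**The concern.** When the allocation ratio changes between two sets of patients, each set is a valid randomised comparison, but the simple pool of the two is not. Here the first cohort supplies most of the active arm and only just over half of the controls. If the cohorts differ in the analysed variable for any reason (case mix, raters, equipment, learning in the delivery of training), part of that difference appears as a treatment effect.

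Estimation is at stake more than testing. The plan will use the observed freezing effect to size future trials. A bias created by the allocation would pass into that figure, and the confidence interval would not reveal it. Because no analysis is named for the primary outcome, the choice between post-treatment values, change scores and adjusted values also stays open until the data have been seen.

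**Working it through.** **Inputs from section D.** Cohort 1: 10 active, 5 control. Cohort 2: 2 active, 4 control. Totals: 10 + 2 = 12 and 5 + 4 = 9. Planned means 0.11 and −0.06, SD 0.10, so the planned effect is 0.17/0.10 = 1.7 SD (Aim 1 connectivity). Two-sided α = 0.05.

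**Assumptions, not in the documents.** The size of any cohort shift; the baseline-to-post correlation ρ; an illustrative true effect of 0.85 SD (half the planned one); 21 evaluable patients.

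**The plan's own figure.** It states 80% power for 12 and 9. With the noncentral t distribution (19 df) these inputs give 95.5%. The first cohort alone (10 and 5) gives 81.8%. This mismatch is a separate matter, and nothing below depends on it.

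**Arm and cohort.** The probability of active treatment is 10/15 = 66.7% in cohort 1 and 2/6 = 33.3% in cohort 2. Cohort 1 makes up 10/12 = 83.3% of the active arm and 5/9 = 55.6% of controls. The arm–cohort correlation has magnitude 0.30.

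**Leak.** Bias of the pooled difference = (10/12 − 5/9) × shift = 0.278 × shift. Type I error is from 200,000 simulated null trials per shift; two separate simulations agree to within about 0.1 percentage point.

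| Assumed shift (SD) | Bias, pooled (SD) | Type I error, pooled | Type I error, with cohort term |
|---|---|---|---|
| 0.25 | 0.07 | 5.1–5.2% | about 5.0% |
| 0.5 | 0.14 | 5.5% | about 5.0% |
| 1 | 0.28 | 6.4–6.5% | about 5.0% |

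With the cohort term the bias is zero in every row. Against the planned 1.7 SD, the pooled biases are 0.07/1.7 = 4%, 0.14/1.7 = 8% and 0.28/1.7 = 16%. That benchmark belongs to Aim 1 only.

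**Price of the cohort term.** Information = Σ n₁n₀/n.
- Pooled: 12×9/21 = 5.143, variance 0.1944 SD², SE 0.44 SD.
- By cohort: 10×5/15 + 2×4/6 = 4.667, variance 0.2143 SD², SE 0.46 SD.
- SE ratio: √(5.143/4.667) = 1.050.
- Power at 1.7 SD: 95.5% pooled (19 df), 93.5% with cohort (18 df).
- Mean squared errors are equal when 0.278² × shift² = 0.2143 − 0.1944, that is 0.0772 × shift² = 0.0198, so shift = 0.51 SD. Below that, the pooled estimate is the more accurate on average.

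**Does baseline adjustment or a change score suffice?** Simulated null trials, ρ = 0.5, bias in SD (absolute value):

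| Analysis | 1 SD level shift (baseline and post) | 1 SD shift in change |
|---|---|---|
| Post-treatment only | 0.28 | 0.28 |
| Change score | 0.00 | 0.28 |
| Arm + baseline | 0.12 | 0.28 |
| Arm + baseline + cohort | 0.00 | 0.00 |

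Only the model with cohort is free of bias in both columns.

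**Power at 0.85 SD, no shift:**

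| Analysis | ρ = 0.3 | ρ = 0.5 | ρ = 0.7 |
|---|---|---|---|
| Post-only t-test | 45% | 45% | 45% |
| Change-score t-test | 34% | 45% | 66% |
| Arm + baseline + cohort | 42% | 49% | 65–66% |

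**Sizing a later trial (1:1, 80% power, two-sample t-test, SD held fixed).** A true effect of 0.85 SD needs 23 per arm. A 0.5 SD shift moves the expected pooled estimate to 0.85 ± 0.14, that is 0.99 or 0.71, giving 18 or 33 per arm. With 18 per arm and a true 0.85 SD, power is 70%.

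**The case against.** The best counter-argument is that the harm is hypothetical and small. The documents report no cohort difference and give little reason to expect one: one clinic, one set of criteria, one intervention and one assessment protocol. Even that the six patients come later is inferred from their being called additional. At shifts up to 0.5 SD the bias is at most 0.14 SD against a sampling SE of 0.44 SD, type I error stays near 5.5%, and pooling has the lower mean squared error. All of that stands.

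Sampling error also dominates the sizing illustration. At a true 0.85 SD with no shift, the middle half of pooled estimates is 0.85 ± 0.674 × 0.44, about 0.55 to 1.15, which translates to 53 down to 13 per arm. With the cohort term it is about 0.54 to 1.16, or 56 down to 13. The adjustment removes a bias; it does not make 21 patients a reliable basis for sizing.

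The t-test is named only for Aim 1 sizing, and change scores may be what is intended. If so, level differences between cohorts cancel, and only a cohort difference in change leaks. That narrows the concern without closing it, since the plan does not say so. It is also fair that the arms are associated with cohort rather than fully confounded with it; this is why an adjusted effect can be estimated at all.

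What does not stand is that adjustment must wait for evidence of a shift. The unequal allocation probabilities are a known feature of the design, and accounting for them is cheap.

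**Conclusion.** The concern holds and should be fixed. It is certain from the text that allocation differs by cohort and that no cohort or baseline adjustment is specified for any outcome. It is arithmetic that an unadjusted pooled analysis passes 27.8% of any cohort difference in the analysed variable into the treatment effect. Whether such a difference exists is unknown; the 0.25 to 1 SD shifts are assumptions, and over that range the bias is 0.07 to 0.28 SD. The effect on type I error is slight. The reason to act is a bias built in by the design, in an estimate the protocol intends to carry into later trials, and not a gain in power. The percentages of the 1.7 SD effect apply to connectivity only, because the protocol says the clinical effect size is not established.

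**What to change.** For each continuous outcome, including dual task interference for turning and PPN–SMA connectivity, prespecify one linear model: post-treatment value on arm, baseline value of the same measure, and randomisation cohort (first 15 versus additional 6). Report the adjusted difference with its 95% confidence interval, and use that figure when sizing future trials. Report the estimate without the cohort term as a sensitivity analysis. The text should also name the medication state, the summary of the two gait trials and the time point that make up the post-treatment value, since gait is recorded off and on medication and the freezing questionnaire is repeated at 1, 2 and 3 months.

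The change is SAP wording only, using data already collected. It costs 5.0% in standard error and about 2 points of power at the planned effect (95.5% to 93.5%) before baseline adjustment, and some mean squared error if the true shift is below about 0.51 SD. Relative to a post-only t-test, baseline adjustment offsets the power loss from about ρ = 0.5.

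The second cohort has only two active patients. Losing one raises the SE penalty to √[(11×9/20)/(10×5/15 + 1×4/5)] = √(4.950/4.133) = 1.094, or 9.4%. Losing both leaves that cohort with no comparison between arms. The SAP should say how that case will be reported.

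### The primary outcome sits under Aim 2, but the trial is sized on an Aim 1 connectivity measure that has no outcome rank; separately, the stated 80% power does not follow from its inputs

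*Combined protocol and SAP*

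**What the plan says.** Section D, Trial Design and outcomes, names one primary outcome: "The primary outcome measure will be dual task interference for turning". The Gait Assessment/Analysis Protocol paragraph then lists the secondary outcomes: dual-task interference for overall task time, step length and velocity, plus the nFOG-Q. No imaging measure is in either list. Gait is recorded both off and on medication, and neither state is assigned to the primary outcome.

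Section A gives Aim 1 a connectivity hypothesis, that stimulation plus rehabilitation "will decrease connectivity between mesencephalic locomotor region (MLR) and SMA more so than rehabilitation alone". Aim 2 is clinical: the combination "will improve FoG severity (as measured by objective and subjective markers of FoG severity". Section C describes turning dual-task interference as an important marker of freezing severity.

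The Statistical analyses paragraph says "The sample size estimation is based on the primary (mechanistic) aim (Aim 1"), and gives the reason: "since the effect size of the clinical aim (Aim 2) has not yet been established". The planned t-test is two-sided at 0.05 and, the plan says, "will have 80% power to detect the difference between a treatment group mean of 0.11 and a control group mean of -0.06". The SD behind that claim is 0.10 and the group sizes are 12 and 9. The means and SD are "based upon the functional connectivity strength for the FOG+ and combined control groups" in a cited publication. The paragraph ends by saying that the observed effects on freezing severity will be used to size future efficacy trials.

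**The concern.** The label primary is attached to an outcome under one aim and to the other aim itself. The measure that justifies 21 participants is ranked neither primary, secondary nor exploratory. If connectivity and turning point in different directions, a reader cannot tell from the plan what standing the connectivity result has. With two medication states recorded and neither chosen, the declared primary outcome also has two possible versions. That matters because the observed clinical effect is meant to feed the design of later trials.

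The power sentence raises a second, independent question: whether 80% follows from the figures given beside it.

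**Working it through.** **Rank, by setting the text side by side**

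| Item | Where | Belongs to |
|---|---|---|
| Only named primary outcome: turning dual-task interference | D, Trial Design and outcomes | Aim 2, because Section C calls it a marker of freezing severity and Aim 2 concerns freezing severity |
| Aim called primary | D, Statistical analyses | Aim 1 |
| Measure behind the sample size: functional connectivity strength | D, Statistical analyses | Aim 1; in no outcome list |
| Secondary outcomes | D, Gait Assessment/Analysis Protocol | Aim 2 measures only |

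Assigning turning to Aim 2 is an inference, but a firm one from Sections A and C. The Imaging Protocol paragraph says how connectivity is acquired and correlated, and gives it no rank.

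**Power, from the plan's own inputs**

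Inputs (Statistical analyses): means 0.11 and -0.06, SD 0.10, groups of 12 and 9, two-sided 0.05, two-group t-test.

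1. Standardised difference: d = (0.11 - (-0.06)) / 0.10 = 0.17 / 0.10 = 1.7.
2. Degrees of freedom: 12 + 9 - 2 = 19; critical value t(0.975, 19) = 2.093.
3. Standard-error factor: sqrt(1/12 + 1/9) = 0.441. Noncentrality: 1.7 / 0.441 = 3.85.
4. Power from the noncentral t distribution: **95.5%**. The normal approximation gives 97.1% and a one-sided test 98.1%. None reproduces 80%.
5. Solving for 80% at 12 versus 9 gives d = 1.302. That is a difference of 1.302 x 0.10 = 0.130 at SD 0.10, or an SD of 0.17 / 1.302 = 0.131 at a difference of 0.17.
6. The Trial Design paragraph first allocates 10 active and 5 control, then adds 6 patients (2 active, 4 control). At 10 versus 5 (df = 13, standard-error factor sqrt(1/10 + 1/5) = 0.548), d = 1.7 gives **81.8%**. The 80% may therefore have been carried over from the 15-patient stage. This is a plausible inference; the documents do not say so.

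**How far 95.5% can be relied on**

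Imaging is done before and after the intervention, and the plan does not say whether 0.10 is the SD of a level or of a change. If it is the SD of a level, equal at both times, and change is analysed, then SD(change) = 0.10 x sqrt(2(1 - r)), where r is the pre/post correlation. The documents give no r, so the values below are assumptions, with the difference held at 0.17 and groups at 12 and 9.

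| Assumed r | SD of change | Power |
|---|---|---|
| 0 | 0.141 | 73% |
| 0.3 | 0.118 | 87% |
| 0.5 | 0.100 | 95.5% |
| 0.7 | 0.077 | 99.7% |

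The planning means also put treatment (0.11) above control (-0.06), whereas Aim 1 predicts a greater decrease with treatment. The sign does not alter two-sided power, but it leaves unclear what the two means represent.

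**Precision for the declared primary outcome**

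The documents give no SD or effect size for turning, so precision can be stated only in SD units. For an unadjusted comparison at 12 versus 9, the 95% CI half-width is 2.093 x 0.441 = 0.92 SD.

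**The case against.** The strongest defence is that only one sentence names a primary outcome measure, and it is clear. The Statistical analyses paragraph ranks an aim, qualifies it as mechanistic, contrasts it with the clinical aim, and explains why sizing rests on it. Sections B and E describe the work as gathering pilot data. A mechanistic basis for sizing beside a clinical primary outcome is defensible in such a study.

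Much of this stands, and it rules out several stronger readings that a reader might infer:

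- *The plan names two primary outcomes.* It does not. It names one primary outcome and, separately, one primary aim.
- *The trial conceals that it is underpowered for turning.* No power is claimed for turning, and the reason is given.
- *The power error shows that 21 is too few.* On the plan's own inputs the error understates power. It is also independent of the rank mismatch: correcting it would leave that mismatch untouched.
- *The MLR hypothesis and the PPN measurements contradict each other.* Section C links PPN-SMA connectivity to the central hypothesis, and the Imaging Protocol includes SMA among the regions correlated with PPN. What is missing is a statement that one represents the other and the choice of one pair from several.

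What the defence does not answer is that explaining the basis for sizing gives connectivity no place among the outcomes, and does not say how a primary aim under Aim 1 relates to a primary outcome under Aim 2.

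**Conclusion.** The point holds as two separate defects, both worth correcting.

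First, there is a mismatch of rank: the sole primary outcome belongs to Aim 2, Aim 1 is called the primary aim, and the measure on which the trial is sized appears in no outcome list. The unassigned medication state adds to the ambiguity. This is a disclosed choice that has been left incompletely labelled.

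Second, the power sentence is wrong as written: its inputs give 95.5% at 12 versus 9, not 80%. This figure assumes a two-sided two-sample t-test with the stated difference and SD taken at face value. A reader might infer that the trial really has 95.5% power for Aim 1, and the documents do not support that either. The inputs come from a comparison of FOG+ patients with controls, not from treatment effects, and no SD for pre/post change is given.

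**What to change.** Make these changes before outcome data are seen by arm:

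1. Keep turning dual-task interference as the primary outcome, reported as an estimate with a 95% CI and no power claim. List one named connectivity measure, the PPN-SMA resting-state correlation, as the mechanistic outcome to which the power statement applies, and state that it represents the MLR-SMA hypothesis.
2. Name one medication state for the primary turning outcome and report the other as secondary. Section C reports that the excess interference in patients with freezing was most marked off medication, so the choice can affect the result.
3. Restate the power sentence so that its inputs and power agree at 12 versus 9: at SD 0.10, either 95.5% for a difference of 0.17 or 80% for about 0.13. Say whether the means and SD are levels or pre/post changes, and in which direction, so that they can be squared with the predicted decrease.

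Promoting connectivity to primary would also align the labels, but it would replace the declared primary outcome. Keeping turning avoids any question of outcome switching.

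The cost is protocol wording, with no new data, visits or participants. The downside is that the declared primary outcome carries no power claim, and the stated power still depends on inputs from a cross-sectional comparison.

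### No between-group model is stated for any outcome: specify ANCOVA on the same measure's baseline with randomisation stage as a covariate, and report the SDs and pre-post correlation that later trials will need

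*Combined protocol and SAP*

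**What the plan says.** Section D, Statistical analyses, is the whole statistical text. It bases the sample size on Aim 1 and names "A two group t-test with a 0.05 two-sided significance level", which "will have 80% power to detect the difference between a treatment group mean of 0.11 and a control group mean of -0.06" with an SD of 0.10 and groups of 12 and 9. The means and SD "are based upon the functional connectivity strength for the FOG+ and combined control groups" in a cited study. For Aim 2 it says only that the observed effects on FoG severity "will be used to determine the effect size of this therapy, and estimate the sample size for future trials". No test, model, covariate or definition of change follows for any outcome.

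Elsewhere in section D:
- The Imaging Protocol repeats the same imaging on either side of the intervention. Its time-course correlations give a connectivity value for each patient, not a group comparison.
- The Gait Assessment/Analysis Protocol measures gait at baseline and afterwards.
- Patient Selection places nFOG-Q at screening and post intervention.
- Trial Design and outcomes makes dual task interference for turning the primary outcome. It randomises 15 patients 10:5 (active:control), then a further 6 at 2:4.

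The section A hypotheses are worded as change: treatment "will decrease connectivity between mesencephalic locomotor region (MLR) and SMA more so than rehabilitation alone" and "will improve FoG severity (as measured by objective and subjective markers of FoG severity) more so than rehabilitation alone".

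**The concern.** Three analyses are open for every outcome: compare post values, compare changes, or compare post values adjusted for baseline. The hypotheses point to change, while the sample-size inputs are connectivity levels. With 12 against 9 patients the three can give visibly different answers, and nothing fixes the choice before the data are seen.

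The estimate itself is the main product of Aim 2, because it is to size later trials. A change score over-corrects a chance baseline difference by (1 - r) times its size, and a post-only comparison leaves r times it in. This is noise, not bias, and planned baseline data can remove much of it.

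The change of allocation ratio is a different matter. Arm is correlated with randomisation stage, so a shift in outcome between the first 15 patients and the additional 6 biases any analysis that ignores stage, unless the shift cancels.

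**Working it through.** **Inputs from the protocol.** Groups 12 and 9; stages 10:5 and 2:4; difference 0.11 - (-0.06) = 0.17; SD 0.10; two-sided 0.05.

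**Assumed.** r = 0.3, 0.5, 0.7; k = baseline SD / post SD = 1 unless stated; a stage shift of 0.5 SD for the bias check.

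**The plan's own figure.** The noncentrality is 0.17 / (0.10 × √(1/12 + 1/9)) = 3.86 on 19 df, which gives 95.5% power, not 80%. At 10 v 5 (13 df) it is 81.8%. That mismatch is a separate point; nothing below depends on it.

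**Chance imbalance.** The SD of the baseline difference is √(1/12 + 1/9) = 0.441 SD, so it exceeds 0.5 SD in about 26% of randomisations.

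**Variance of the arm difference, in units of post SD²**
- Post-only: 1/12 + 1/9 = 0.1944.
- Change score: (1 + k² - 2rk) × 0.1944, which is 2(1 - r) × 0.1944 at k = 1.
- ANCOVA, baseline only: (1 - r²) × (18/17) × 0.1944. The factor 18/17 is the cost of estimating the slope.
- ANCOVA, baseline and stage: (1 - r²) × (17/16) / 4.67. Here 4.67 = 10×5/15 + 2×4/6 is the within-stage information, against 12×9/21 = 5.14 without stage.

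| | r = 0.3 | r = 0.5 | r = 0.7 |
|---|---|---|---|
| Post-only | 0.194 | 0.194 | 0.194 |
| Change score | 0.272 | 0.194 | 0.117 |
| ANCOVA, baseline only | 0.187 | 0.154 | 0.105 |
| ANCOVA, baseline + stage | 0.207 | 0.171 | 0.116 |
| Baseline only v change | -31% | -21% | -10% |
| Baseline only v post-only | -4% | -21% | -46% |
| With stage v change | -24% | -12% | under -1% |
| With stage v post-only | +7% | -12% | -40% |

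**Unequal SDs.** At k = 0.8 the change-score factor is 1.16, 0.84 and 0.52. ANCOVA with stage then has 8% lower, 5% higher and 15% higher variance than the change score.

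**Worst case.** Since 1 + k² - 2rk ≥ 1 - r², the baseline-only loss cannot exceed 18/17 - 1 = 5.9%. With stage it cannot exceed (17/16) × (5.14/4.67) - 1 = 17%. Both bounds assume a normal baseline and a common linear slope.

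**Why stage belongs in the model.** Stage 1 supplies 10/12 = 83% of active but 5/9 = 56% of control patients, a gap of 0.278. A 0.5 SD stage shift in the post value alone gives a bias of 0.278 × 0.5 = 0.14 SD in both baseline-only ANCOVA and the change score. If baseline and post shift equally, the change score is unbiased, while simulation gives baseline-only ANCOVA a bias of 0.09, 0.07 and 0.04 SD at the three values of r. The stage term removes the bias in both cases.

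**Power at the Aim 1 effect (0.17, SD 0.10).** Post-only 95.5%. Change score 87.1%, 95.5%, 99.7%. Baseline-only ANCOVA (18 df) 96.0%, 98.3%, 99.9%. ANCOVA with stage, noncentrality 0.17 / (0.10 × √V) on 17 df with V from the table: 94.0%, 97.2%, 99.7%.

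**Precision at r = 0.5, SD taken as known.** The 95% half-width is 2.110 × √0.171 = 0.87 SD with stage, against 2.093 × √0.194 = 0.92 SD for either unadjusted analysis.

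**The case against.** The strongest reply is that the t-test is a sample-size basis, not an analysis commitment, so the gains are measured against analyses the plan never adopts. That stands. A reader might infer that the trial is committed to an unadjusted t-test, on changes or on post values; the text commits to neither.

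Nor is r in the documents. The primary outcome contrasts single- and dual-task performance from two trials each, so a low r cannot be excluded. That also stands. By the formulae above, with equal SDs, the stage model loses to post-only when r is below √(1 - 0.1944 × 4.67 × 16/17) = 0.38. It loses to the change score when r is above 2 × 0.1944 × 4.67 × 16/17 - 1 = 0.71.

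A further temptation is to quote the 6% ceiling as the whole cost and leave stage optional. The changed allocation ratio does not allow that: the baseline-only model keeps the stage bias, and removing it raises the ceiling to 17%. A change score can do better if stage shifts baseline and post equally, but nothing in the documents supports counting on that.

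Pilot status is the weaker defence. An estimate intended to size later trials needs its estimator fixed in advance.

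**Conclusion.** The omission is certain on the text, and the remedy is a specific model using data already planned. The size of the benefit is conditional on r, on the SD ratio and on what the analyst would otherwise have done. Over the assumed r with equal SDs, ANCOVA with stage ranges from 40% lower to 7% higher variance than the unadjusted alternatives. With a smaller baseline SD it can be 15% higher than a change score.

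At the plan's Aim 1 effect little power is at stake. The case rests on the Aim 2 estimates, and on settling the estimator and the stage question before the data are seen. A reader might infer that chance imbalance biases the trial, or that adjustment makes 12 v 9 precise enough for planning. Neither follows: randomisation covers the first within each stage, and an interval of about ±0.87 SD rules out the second. The change should be made, but the trial does not fail without it.

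**What to change.** In section D, Statistical analyses, state that each of the following will be analysed by ANCOVA of the post-intervention value on arm, the same measure's baseline and randomisation stage (10:5, then 2:4):
- dual task interference for turning (primary);
- dual task interference for overall task time, step length and velocity;
- nFOG-Q at the post-intervention visit;
- PPN-SMA connectivity, the imaging measure that serves the MLR-SMA hypothesis.

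For each, report the adjusted difference with 95% CI. Also report the baseline and post SDs by arm and the pre-post correlation, so that a later trial can standardise the effect and choose its own analysis.

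The cost is a few sentences and two residual df (19 to 17). Relative to the better unadjusted analysis, it may also cost up to about 17% in variance in the worst case. No new data are needed.

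Medication state, averaging of trials, the phone nFOG-Q visits, DKI, TMS/BOLD and the 80% power figure are separate points that this change does not settle.
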